8.3. Clinical Laboratory Tests

8.3.1. Laboratory Value Definitions

Laboratory values and change from baseline values will be summarized descriptively by visit. Baseline will be determined according to Section 4.2.3. If there are multiple values that meet the criteria for baseline, additional rules may be provided after consultation with the medical monitor to delineate which value will be defined as baseline.

Laboratory test values outside the normal range will be assessed for severity based on CTCAE grade or similar criteria where clinical intervention is required for CTCAE grading. The incidence of abnormal laboratory values and shift tables relative to baseline will be tabulated.

8.3.2. Laboratory Value Summaries

All test results and associated normal ranges from central laboratories will be reported in SI units. All tests with numeric values will have a unique unit per test. Any laboratory test results and associated normal ranges from local laboratories will be converted to SI units. For the limited number of cases where the associated normal ranges from a local laboratory cannot be obtained despite due diligence, associated central laboratory normal ranges will be applied. In the event that central laboratory normal ranges are not available, a set of standard normal ranges based on documented reference ranges will be applied to facilitate reporting the test results.

When there are multiple laboratory nonmissing values for a subject's particular test at a scheduled visit, central laboratory values have higher priority over local laboratory values. If a tie still exists, the laboratory value with the smallest laboratory sequence number will be used in by-visit summaries.

Numeric laboratory values will be summarized descriptively in SI units, and non-numeric test values will be tabulated when necessary.

For test results that will be summarized with available normal ranges, the number and percentage of subjects with the laboratory values being low (but never high), normal, high (but never low), and both low and high will be calculated for each test. This shift summary will be produced for each test for the safety population. The denominator for the percentage calculation will use the number of subjects in the baseline category (ie, low, high, normal, missing) as the denominator for the percentage in each of the categories during the treatment period.

Shift tables will be presented showing change in CTCAE grade from baseline to worst grade postbaseline. Separate summaries for abnormally high and abnormally low laboratory values will be provided when the laboratory parameter has both high and low grading criteria. The denominator for the percentage calculation will be the number of subjects in the baseline category.

In cases where differentials of hematology parameters are obtained without corresponding absolute count data, efforts will be made to investigate if the conversion to an absolute value will lead to additional abnormalities. This will be discussed with the clinical team regarding appropriate documentation and action.

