1.8.3. Risks From Azacitidine

Azacitidine is known to be associated to cytopenias including anemia, neutropenia, and thrombocytopenias. Subjects will have complete blood counts performed at baseline and 2 additional times per cycle in Cycle 1 and 2 in Part 1 dose escalation. Potential safety concerns and recommended management guidelines regarding hematologic toxicities, hepatotoxicity, renal abnormalities, and other toxicities of concern are summarized in the azacitidine approved label.

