"_____ azacitidine in clinic"		X	X		X	X		X			• Five doses of azacitidine will be administered in the clinic on D1-D7 of Cycles 1 through 3.
"_____ epacadostat in clinic"		X			X					r <>ll<tion on C1DI and C2DI.	
"_____ pembrolizumab in clinic"		X			X			X			
EFFICACY ASSESSMENTS											
Radiologic tumor assessments	X							X	X		• Every 9 weeks (63 ± 7 days) until disease progression. After 12 months of study treatment, imaging frequency may be reduced to every 12 weeks. Imaging should not be delayed for delays in cycle starts or extension of combination treatment cycle intervals.

Table 30: Laboratory Assessments (Treatment Group A: Part 1 and Part 2 Expansion Cohorts A-1 and A-2)

Laboratory Assessment Window	Screening	Treatment							EOT	Safety Follow-Up	Notes
		C1 D1	C1 D5-7	C1 D15	C2 D1	C2 D5-7	C2 D15	C3+ D1			
	Day -28 to Day-1	D1	D5-7	±3 d	±3 d	D5-7	±3 d	±3 d	+5 d	EOT+ 42-49 d	
LOCAL LABORATORY TESTS											
Comprehensive senun chemistry	X	X	X*	X	X	X*	X**	X	X	X	* Visit to occur on the fifth day of azacitidine dose administration. ** Cycle 2 Day 15 visits are not required for subjects in Part2.
Hematology with differential	X	X	X*	X	X	X*	X**	X	X	X	* Visit to occur on the fifth day of azacitidine dose administration. ** Cycle 2 Day 15 visits are not required for subjects in Part2.
HgbA1c	X										
Coagulation panel	X				X			X*	X		*Only at Cycles 4, 7, 10, etc.
Endocrine panel	X				X			X*	X		* Only at Cycles 4, 7, 10, etc.
U!nalysis	X				X			X*			* Only at Cycles 4, 7, 10, etc.
Senun pregnancy test	X*									X	* A senun pregnancy test will be required for all women of childbearing potential during screening and must be performed within 72 hours before the first dose of study dmg.
Serology											
CEA/CA19-9*		X			X			X**	X		* CEA to be petforned in subjects with CRC only. CA 19-9 to be performed in subjects with pancreatic cancer only. ** CEA and CA 19-9 will be collected every other cycle aftet C2.

Table 30: Laboratory Assessments (Treatment Group A: Part 1 and Part 2 Expansion Cohorts A-1 and A-2) (Continued)

Laboratory Assessment Window	Screening	Treatment							EOT	Safety Follow-Up	Notes
		C1 D1	C1 D5-7	C1 D15	C2 D1	C2 D5-7	C2 D15	C3+ D1			
	Day -28 to Day -1	D1	D5-7	± 3 d	± 3 d	D5-7	± 3 d	± 3 d	+ 5 d	EOT + 42-49 d	

Table 31: Schedule of Assessments (Treatment Group A: Part 2 Expansion Cohort A-3, Azacitidine Monotherapy Lead-In)

Visit Day	Screening	Treatment					EOT	Safety Follow-Up	Notes
		Week-1	C1 D1	C2 D1	C2 DS-7	C3+ D1			

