LOCAL LABORATORY TESTS									
Comprehensive serum chemistry	X	X	X	X	X	X	X	X	
Hematology with differential	X	X	X	X	X	X	X	X	
HgbA1c	X								
Coagulation panel	X			X			X*	X	* Only at Cycles 4, 7, 10, etc
Endocrine panel	X			X			X*	X	* Only at Cycles 4, 7, 10, etc
Urinalysis	X			X			X*		* Only at Cycles 4, 7, 10, etc
Serum pregnancy test	X*							X	* A serum pregnancy test will be required for all women of childbearing potential during screening and must be performed within 72 hours before the first dose of study drug.
Serology	X								

Table 33: Schedule of Assessments (Treatment Group A: Part 2 Expansion Cohort A-4, Pembrolizumab/Epacadostat Lead-In)

Visit Day	Screening	Treatment				EOT	Safety Follow-Up	Notes
		C1 DI	C2 DI	C2 DS-7	C3+ DI			
Evaluation Window	Day -28 to Day-1	DI	± 3 d	DS-7	±3 d	+Sd	EOT + 42-49 d	
ADMINISTRATIVE PROCEDURES								
Informed consent	X							
Contact iRT	X	X	X		X	X		
Inclusion/exclusion criteria	X	X						
Medical and cancer history	X							
Prior/concomitant medications	X	X	X	X [•]	X	X	X	• Visit to occur on the fifth day of azacitidine dose administration.
Distribute reminder cards	X	X	X	X [•]	X	X		• Visit to occur on the fifth day of azacitidine dose administration.
Study drug dispensing		X	X		X			
Assess study drug compliance			X		X	X		
CLINICAL PROCEDURES AND ASSESSMENTS								
Physical examination/body weight and height*	X	X	X	X ^{••}	X	X	X	• Comprehensive examination at screening, targeted physical examination thereafter. Height at screening only. •• Visit to occur on the fifth day of azacitidine dose administration.
Vital signs	X	X	X	X [•]	X	X	X	• Visit to occur on the fifth day of azacitidine dose administration.
ECOG performance status	X	X	X	X [•]	X	X	X	• Visit to occur on the fifth day of azacitidine dose administration.

Table 33: Schedule of Assessments (Treatment Group A: Part 2 Expansion Cohort A-4, Pembrolizumab/Epacadostat Lead-In) (Continued)

Visit Day	Screening	Treatment				EOT	Safety Follow-Up	Notes
		C1 DI	C2 DI	C2 DS-7	C3+ DI			
Evaluation Window	Day -28 to Day -1	DI	± 3 d	DS-7	±3 d	+ S d	EOT + 42-49 d	

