5.2. Treatment Groups

This is an open-label, multicenter, Phase 1/2 study evaluating the addition of an epigenetic priming regimen to an immunotherapy doublet in subjects with advanced or metastatic solid tumors. The study will be conducted in 2 parts.

Due to the stop of study enrollment, only subjects in Treatment Group A have been enrolled into Parts 1 and 2. Data from Parts 1 and 2 for Treatment Group A will be summarized together by dose level. The dose levels for Treatment Group A are shown in [Table 1](#).

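### Day 15 blood counts are scheduled 2, 1 or 0 times depending on cohort, yet the SAP pools Parts 1 and 2 by dose level for worst-grade hematology shifts, so the expansion-dose column may understate cytopenias

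*SAP*

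**What the plan says.** On analysis, SAP 8.3.2 plans that "Shift tables will be presented showing change in CTCAE grade from baseline to worst grade postbaseline". SAP 5.2 sets the columns: "Data from Parts 1 and 2 for Treatment Group A will be summarized together by dose level". SAP Appendix A lists the hematology version as Table 3.3.2, on the safety population and marked for in-text use. Protocol 9.4.4.2 counts each subject once, at the worst grade seen after baseline. Neither document limits worst grade to visits shared by all cohorts, splits it by Part, or notes that schedules differ.

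On sampling, Protocol 1.8.3 names cytopenias as the known azacitidine risk and promises "complete blood counts performed at baseline and 2 additional times per cycle in Cycle 1 and 2 in Part 1 dose escalation". Protocol Table 30, which covers Part 1 and A-1/A-2, has Day 15 columns in Cycles 1 and 2, but its hematology row carries the note "Cycle 2 Day 15 visits are not required for subjects in Part2". Tables 32, 34 and 36 (A-3, A-4, A-5) have no Day 15 column. All cohorts do have a count tied to the azacitidine course, noted as "Visit to occur on the fifth day of azacitidine dose administration" in Table 30 and similarly for the sequencing cohorts. From Cycle 3 every cohort has scheduled counts on Day 1 only.

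**The concern.** A worst grade is an extreme taken over however many counts a subject happens to have. Protocol 4.1.2.1 runs the Treatment Group A expansion at the recommended Phase 2 dose, so Part 2 subjects collect in that one dose column, while the other dose levels hold only Part 1 subjects with the densest early schedule. A by-dose reading of Table 3.3.2 then mixes dose with sampling intensity. The expansion dose is also the one whose hematologic safety will be read most closely. A dip that begins after the dosing week and recovers before the next Day 1 can enter the table for a Part 1 subject and leave no trace for an A-4 subject.

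**Working it through.** **Step 1: the plan's own figure.** Protocol 1.8.3 states 2 extra counts per cycle in Part 1, Cycles 1 and 2. Table 30 gives Day 5-7 plus Day 15, which is 2. It reproduces.

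**Step 2: scheduled counts after first dose, through Cycle 3 Day 1** (Tables 30, 32, 34, 36; the A-3 Week -1 count is placed on the fifth azacitidine day by Table 31).

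| Cohort | All counts | Fifth-azacitidine-day | Day 15 |
|---|---|---|---|
| Part 1 | 6 | 2 | 2 |
| A-1/A-2 | 5 | 2 | 1 |
| A-3 | 5 | 2 | 0 |
| A-4/A-5 | 3 | 1 | 0 |

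In A-3, azacitidine starts in Week -1, so the Cycle 1 Day 1 count falls at about Day 8 of the azacitidine course. It is not a Day 15 count, but it is a look after the dosing week. A-4 and A-5 start azacitidine in Cycle 2, so by Cycle 3 Day 1 they have had one course only.

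**Step 3: an illustration of size.** Let q be the chance per cycle of a Grade 3 or higher count visible on Day 15 only. The documents give no value, so q = 5% to 30% is assumed, equal at all doses. With k Day 15 looks, the chance of detection is 1 - (1 - q)^k. At q = 10% this is 1 - 0.9² = 19% in Part 1 (k = 2), 10% in A-1/A-2 (k = 1) and 0% in A-3 to A-5 (k = 0).

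Cohort sizes are planned ones: 3 to 9 per dose level in Part 1 (Protocol 9.2.1.1), and 16 to 54 in A-1/A-2 with 60 in A-3 to A-5 (Protocol 4.3.1). The last two columns below give detection at the pooled expansion dose as a share of a Part 1-only dose level, over q = 5% to 30%.

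| Assumed mix (Part 1 + A-1/A-2 + A-3 to A-5) | Pooled detection at q = 10% | Share, A-3 given no look | Share, A-3 (25 subjects) given one look |
|---|---|---|---|
| 6 + 16 + 0 | (6×19% + 16×10%)/22 = 12.5% | 65-70% | 65-70% |
| 6 + 16 + 60 | (6×19% + 16×10%)/82 = 3.3% | 17-19% | 33-37% |
| 9 + 54 + 60 | (9×19% + 54×10%)/123 = 5.8% | 30-33% | 40-45% |

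These shares concern only events visible on Day 15 alone. Events that other counts also pick up narrow the gap. With an assumed 10% background seen equally in every cohort, and q = 10%, Part 1 shows 1 - 0.9×0.81 = 27.1%. The first mix shows 1 - 0.9×(1 - 0.1245) = 21.2%, a ratio of 0.78.

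**Step 4: dependence on episode length.** Assume onset uniform on Days 8-16. Day 15 plus the next Day 1 (Day 22) catches 62.5%, 100% and 100% of episodes lasting 5, 7 and 10 days. Day 22 alone catches 0%, 12.5% and 50%. At 12 days Day 22 alone catches 75%, and at 14 days 100%, where the gap closes. Unscheduled counts are ignored here.

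**Step 5: exposure in the other direction.** With an assumed 5% chance per azacitidine cycle of a low count visible on the next Day 1, detection is 1 - 0.95² = 9.8% over 2 cycles and 1 - 0.95⁶ = 26.5% over 6.

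**The case against.** The strongest reply is that the table is descriptive and carries no decision. The MTD is set by DLTs (Protocol 5.4.1.1, SAP 8.2.3), and no test compares shift tables across doses. By-visit hematology summaries, full and abnormal-value listings, and Grade 3 or 4 TEAE tables are also planned. That limits the consequence, and it stands. It does not repair Table 3.3.2: by-visit summaries leave the worst-grade table unchanged, and under Protocol 8.1.1 a laboratory abnormality is an AE only if it is symptomatic, clinically meaningful, or requires therapy or a change in study drug.

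A reader might go further and infer that the expansion dose will look less myelotoxic because its nadirs go unsampled. The documents do not support that:

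- They give no nadir timing or duration.
- A-1/A-2 have a Cycle 1 Day 15 count, Part 1 subjects at the expansion dose have both, every expansion cohort has a count on the fifth azacitidine day, and A-3 has its Cycle 1 Day 1 count.
- Unscheduled assessments are recorded (Protocol 6.6), and Table 15 holds azacitidine for Grade 3-4 hematologic toxicity until it resolves, which should prompt further counts.
- From Cycle 3 Part 1 is sampled no more densely than Part 2.
- The dose-level table lists azacitidine in Cycles 1 and 2, while current text allows up to 6 cycles and the amendment log records the rise from 2 to 6. If earlier Part 1 subjects had fewer cycles, Part 2 subjects had more chances to reach a bad worst grade.

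Actual Part 2 numbers are also absent. SAP 9 says the study ended before the Part 2 interim analyses, so the larger planned mixes above may be far from what was enrolled.

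**Conclusion.** The non-comparability is real and visible in the schedules: 2, 1 or 0 Day 15 counts feed one pooled worst-grade table by dose level, with no split, common-visit rule or caveat. At equal true toxicity and exposure the effect can only run one way, so the expansion-dose column may understate Grade 3-4 cytopenias relative to Part 1-only dose levels. For events visible only on Day 15, the illustration puts detection at 17% to 70% of the Part 1 level. This rests on the assumed q and the planned cohort mixes, and the gap in the total Grade 3-4 rate would be smaller. Neither the size nor the net direction can be fixed from the documents. A possible difference in azacitidine cycles between Parts makes the sign less certain, but it is a second reason not to pool. The point concerns the reported safety comparison and is a cheap improvement, not a flaw in a formal decision.

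**What to change.** In SAP 8.3.2 and Table 3.3.2, present the hematology worst-grade shift by dose level for Part 1 subjects, with separate columns for A-1/A-2 and for A-3 to A-5. Add a footnote giving each cohort's scheduled count days. Keep every observed count, scheduled or not, in the worst grade. Restricting worst grade to Day 1 counts would equalize the schedules but throw away low counts that were actually seen, so it is not recommended. The change needs SAP wording and extra table columns, and no new data or visits. The cost is smaller denominators per column.

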8.4. Vital Signs

Values at each scheduled visit, change, and percent change from baseline for vital signs, including pulse, systolic blood pressure, diastolic blood pressure, respiration rate, body temperature, and weight will be summarized descriptively.

Criteria for clinically notable vital sign abnormalities are defined in [Table 13](#). The abnormal values for subjects exhibiting clinically notable vital sign abnormalities will be listed along with their assigned treatment group. Alert vital signs are defined as an absolute value outside the defined range and percentage change from baseline greater than 25%. The abnormal values for subjects exhibiting alert vital sign abnormalities will be listed.

Table 13: Criteria for Clinically Notable Vital Sign Abnormalities

Parameter	High Threshold	Low Threshold
Systolic blood pressure	> 155 mmHg	< 85 mmHg
Diastolic blood pressure	> 100 mmHg	< 40 mmHg
Pulse	> 100 bpm	< 45 bpm
Temperature	> 38°C	< 35.5°C
Respiratory rate	> 24/min	< 8/min

8.5. Electrocardiograms

Twelve-lead ECGs including RR, QRS, QT, QTcF, QTcB, and JTc intervals will be obtained for each subject during the study. Values at each scheduled visit, change, and percent change from baseline will be summarized for each ECG parameter. Baseline will be determined as the average of all nonmissing values before the first administration of epacadostat, pembrolizumab, or azacitidine.

Criteria for clinically notable ECG abnormalities are defined in Table 14. Subjects exhibiting clinically notable ECG abnormalities will be listed with study visit and assigned treatment group. Abnormal values for subjects with alert ECG values, defined as both the absolute value and the percentage change from baseline being outside normal ranges, will be identified and listed.

Table 14: Criteria for Clinically Notable Electrocardiogram Abnormalities

Parameter	High Threshold	Low Threshold
QTcF	> 460 ms	< 295 ms
PR	> 220 ms	< 75 ms
QRS	> 120 ms	< 50 ms
QT	> 500 ms	< 300 ms
RR	> 1330 ms	< 600 ms

QTcF = Fridericia correction.

Twelve-lead ECGs will be obtained for each subject during the study. Electrocardiogram abnormalities, both at baseline and postbaseline visits, will be tabulated by dose level for Treatment Group A in Parts 1 and 2 combined. Incidences of abnormalities will be listed with study visit, assigned treatment group, and a description of the abnormality.

9. INTERIM ANALYSES

There are no planned, formal interim analyses for Part 1. Periodic review of accrued clinical data will be conducted by the sponsor and provided to study investigators via teleconferences. Based on review of the most current safety data, the sponsor (in consultation with the study investigators and using the dose-escalation/de-escalation rules) will determine if and at what dose additional subjects should be treated in the study.

Since the study was terminated prior to the interim analyses, no interim analyses will be conducted for Part 2.

10. CHANGES AND MODIFICATIONS TO THE ANALYSIS PLAN

All versions of the SAP are listed in [Table 15](#).

Table 15: Statistical Analysis Plan Versions

SAP Version	Date
Original	12 JAN 2018
Amendment 1	18 JUL 2018

10.1. Changes to Protocol-Defined Analyses

10.1.1. Efficacy Analyses

- The efficacy endpoints will only be summarized per RECIST v1.1. [REDACTED]
- The confirmation of responses will not be included.

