7.6.1.2. Tumor Imaging During the Study

Tumor imaging may be performed by CT or MRI, but the same imaging technique should be used in a subject throughout the study. Scans must be a contrast CT or MRI, except in circumstances where there is a contrast allergy or with medical monitor approval. A PET/CT scan that uses higher energy and thinner slices for the CT component may be acceptable (with medical monitor approval) if it was the same technique used for baseline. Imaging should be performed every 9 weeks (63 days \pm 7 days) or more frequently if clinically indicated. After 12 months of study treatment, imaging frequency may be reduced to every 12 weeks. Imaging should not be delayed for delays in cycle starts or extension of combination treatment cycle intervals.

Imaging should continue to be performed until documented disease progression, the start of new anticancer treatment, withdrawal of consent, death, or the end of the study, whichever occurs first. Disease progression should be confirmed at least 4 weeks and not later than 8 weeks after the first scan indicating PD in clinically stable subjects. Subjects who have unconfirmed disease progression may continue on treatment until progression is confirmed provided that they have met the conditions detailed in Section 7.6.1.

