9.4.4.5. Adverse Events of Special Interest

Adverse events of special interest include irAEs that are seen with immunotherapy and any other observed autoimmune phenomenon.

An overall summary of irAEs will include number (%) of subjects reporting any irAEs, any Grade 3 or 4 irAEs, any treatment-related irAEs, any fatal irAEs, and any irAEs leading to treatment interruption/dose reduction/discontinuation.

9_5_ Analyses for the Data Monitoring Committee

Not applicable.

9_6_ Interim Analysis

In Part 2, there will be a planned interim analysis for futility in Expansion Cohorts A-1, A-2, B-7, B-8, C-9, and C-10. The Simon 2-stage design will be applied to each safety/efficacy expansion cohort independently. During Stage 1, 8 NSCLC subjects who progressed on a PD-1 pathway-targeted agent and 8 MSS CRC subjects will be enrolled. If no responses are observed in the NSCLC PD-1 failure and MSS CRC cohorts, the cohort will be terminated for futility. If at least 1 response is observed in the NSCLC PD-1 failure or MSS CRC cohort, 19 additional NSCLC PD-1 failure or MSS CRC subjects will be enrolled for Stage 2 evaluation.

Based on this early termination rule, the probability of early termination is 0.7837 for subjects with NSCLC who are PD-1 failures and subjects with MSS CRC under the assumption of historical control response rate; the probability of early termination is 0.1678 for subjects with NSCLC who are PD-1 failures and subjects with MSS CRC under the assumption of desired response rate.

The interim analysis for each expansion cohort will be conducted once the first postbaseline radiologic tumor assessments for Stage 1 subjects within the cohort are available. Enrollment will be held at that time unless a sufficient number of responders have been observed before that time.

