2.3.1. Primary Endpoints

- Part 1: Safety and tolerability will be assessed by monitoring the frequency, duration, and severity of AEs; through physical examinations; by evaluating changes in vital signs and ECGs; and through clinical laboratory blood and urine sample evaluations.
- Part 2: Objective response rate, defined as the percentage of subjects having a CR or PR, will be determined by investigator assessment of radiographic disease as per RECIST v1.1.

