3.4.2. Sample Size in Part 2 Safety/Efficacy Expansion Cohorts

3.4.2.1. Part 2 Simon 2-Stage Cohorts

The safety/efficacy expansion in Part 2 will include 2 cohorts per treatment group, subjects with NSCLC who have had disease progression on a prior PD-1 pathway-targeted agent and subjects with MSS CRC. A Simon 2-stage design will be used for each of the cohorts (Simon 1989). The response rates for the historical control (p_0), desired response rates for the combination (p_1), number of subjects needed in Stage 1 (n_1) and Stage 2 (n_2), total number of subjects (n), first

stage threshold declaring cohort undesirable (r_1), and the upper limit of the number of responses in n subjects such that futility of the drug is concluded (r) are provided for each expansion cohort in [Table 10](#). The calculation is based on a 1-sided Type I error of 0.05 and power of 80%.

Table 10: Simon 2-Stage Design

Cohort	Tumor Type	p_0	p_1	n_1	n_2	n	r_1	r
Expansion Cohort A-1	NSCLC subjects who have had disease progression on a prior PD-1 pathway-targeted agent	3%	20%	8	19	27	0	2
Expansion Cohort A-2	MSS CRC	3%	20%	8	19	27	0	2
Expansion Cohort B-7	NSCLC subjects who have had disease progression on a prior PD-1 pathway-targeted agent	3%	20%	8	19	27	0	2
Expansion Cohort B-8	MSS CRC	3%	20%	8	19	27	0	2
Expansion Cohort C-9	NSCLC subjects who have had disease progression on a prior PD-1 pathway-targeted agent	3%	20%	8	19	27	0	2
Expansion Cohort C-10	MSS CRC	3%	20%	8	19	27	0	2

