7.2.2. Objective Response Rates and Best Overall Response

A subject is defined as an objective responder if the subject has an overall response of CR or PR at any postbaseline visit prior to first PD. Objective responders will be assessed based on RECIST v1.1.

Objective response rate is defined as the proportion of subjects with objective responses. Objective response rate will be estimated with 95% CIs overall by cohort-specific tumor type. CIs will be calculated based on the method for Simon 2-stage CIs of response rates outlined in Koyama and Chen (2008). Subjects who do not have sufficient baseline data to ascertain response will be included in the denominators in the calculation of ORR.

In general, the best response is determined on subject level using the highest overall response achieved postbaseline prior to and including the first PD, in the order of CR, PR, SD, PD, and NE. Responses of CR, PR, or SD after a response of PD will not be considered in determining best response by RECIST v1.1 criteria. In the case of SD, measurements must meet the SD criteria at least after the date of first dose at a minimum of 56 days (9 weeks – 7-day window). Subjects who fail to meet this criterion will have best overall response of PD if the next available assessment indicated PD, or NE if there is no additional assessment available.

Under RECIST v1.1, the best response is determined by subject using the highest overall response achieved postbaseline prior to and including the first PD, in the order of CR, PR, SD, PD, and NE. Responses of CR, PR, or SD after a response of PD will not be considered in determining best response by RECIST v1.1 criteria. In the case of SD, measurements must meet the SD criteria at least after the date of first dose of study drug at a minimum of 56 days (9 weeks – 7-day window). Subjects who fail to meet this criterion will have best overall

response of PD if the next available assessment indicated PD, or NE if there is no additional assessment available.

For subjects with measurable disease at baseline, the RECIST v1.1 assessment criteria presented in [Table 11](#) can be used to determine the overall disease status at a given time point based on the target lesion, nontarget lesion, and new lesion assessment.

Table 11: RECIST Evaluation Criteria for Overall Response: Measurable Disease at Baseline

Target Lesions	Nontarget Lesions	New Lesions	Overall Response
CR	CR	No	CR
CR	Non-CR/Non-PD	No	PR
CR	NE	No	PR

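### ORR counts unconfirmed, single-scan responses: label it as such and report the confirmed rate beside it as a sensitivity analysis

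*SAP*

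**What the plan says.** The Part 2 primary endpoint is ORR, which "will be determined by investigator assessment of radiographic disease as per RECIST v1.1" (SAP 2.3.1). SAP 7.2.2 defines an objective responder as a subject who "has an overall response of CR or PR at any postbaseline visit prior to first PD". One qualifying scan is enough. The same section does set a persistence condition for stable disease (at least 56 days from first dose), but none for CR or PR.

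SAP 10.1.1, under the heading for changes to protocol-defined analyses, states: "The confirmation of responses will not be included".

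The efficacy analysis that remains is an ORR estimate with a 95% CI (SAP 7.2.2) and a Kaplan-Meier median for DOR (SAP 7.2.3). DOR runs from the earliest response to progression or death (SAP 2.3.2). SAP 10.1.3 says the Simon two-stage design will not be performed because the study ended early, and SAP 9 cancels the Part 2 interim analyses. Overall response at each visit is to be listed (Listing 2.6.3).

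**The concern.** The primary efficacy estimate rests on local readings in an unblinded study with no control arm. A partial response on one scan may reflect measurement variation and be gone at the next scan, yet it counts in full. An error of this kind moves the rate in one direction only, upward.

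DOR is affected too. A one-scan response followed by progression at the next 9-week scan enters as a duration of about 63 days. A responder whose response scan is also the last valid scan, and who has no recorded death, is censored at that scan under SAP Table 12, so contributes almost no follow-up.

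At stake is how a reader takes the ORR. Table 2.1.1 as planned carries no label saying that the responses are unconfirmed, and no companion figure shows how many held.

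**Working it through.** **1. The plan's own design figures.** SAP Table 10 gives the same inputs for every Simon cohort, for example "MSS CRC 3% 20% 8 19 27 0 2": p0 = 3%, p1 = 20%, n1 = 8, n2 = 19, n = 27, r1 = 0, r = 2. The stated one-sided alpha is 0.05 and the power 80%.

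- Early termination: 0.97^8 = 0.7837 at p0 and 0.80^8 = 0.1678 at p1. Both match Protocol 9.6.
- Chance of passing the rule: the sum over x = 1 to 8 of b(x; 8, p) × P(Bin(19, p) ≥ 3 − x).
- At p = 0.03: 0.19392 × 0.10996 + 0.02099 × 0.43939 + 0.00135 = 0.02132 + 0.00922 + 0.00135 = 0.0319.
- At p = 0.20 the same sum is 0.8002.

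The design is sound as stated. It describes a rule that SAP 10.1.3 says will not be applied.

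**2. Direction of the effect.** Divide the responders under SAP 7.2.2 (U) into three groups:

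- C: CR or PR repeated at the next scheduled scan;
- F: a later evaluable scan exists and does not repeat the response;
- M: no later evaluable scan.

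Then U = C + F + M. With the same denominator n, unconfirmed ORR − confirmed ORR = (F + M)/n ≥ 0. The reported ORR cannot be below the confirmed one.

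**3. Size.** Neither document gives F, M or a confirmation ratio, so no value can be computed. What can be stated is the step per subject: 1/8 = 12.5 percentage points and 1/27 = 3.7 points. These are planned cohort sizes; the documents do not give the numbers enrolled.

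**4. Is the later scan available?** Protocol 7.6.1.2 schedules imaging every 9 weeks (every 12 weeks is allowed after 12 months of treatment) until progression, new anticancer therapy, withdrawal of consent, death or end of study. A responder still on treatment will normally have a next scan. The protocol synopsis and section 5.5.2 say that disease follow-up after treatment is no longer required under Amendment 4. M may therefore be above zero for reasons unrelated to the quality of the response. The part of the difference due to responses that failed to hold lies between F/n (if every M response would have been confirmed) and (F + M)/n (if none would).

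**The case against.** A reader might infer that dropping confirmation inflates a test against 3%. SAP 3.3 still states a 0.05 Type I error, Table 10 still shows p0 = 3%, and SAP 7.2.2 still uses a Simon-type CI. The arithmetic is easy to produce. If 1%, 2% or 3% of true non-responders were assumed to show a spurious PR, the apparent null rate becomes 0.03 + 0.97 × 0.01, 0.02 or 0.03, that is 4.0%, 4.9% or 5.9%. The two-stage rule would then pass with probability 0.063, 0.104 or 0.152 instead of 0.032.

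The documents do not support that reading, for three reasons. The rule is withdrawn, so the final analysis has no such error rate. The 1% to 3% figures come from no document. The documents do not say whether the 3% is a confirmed or an unconfirmed rate, so comparing it with a confirmed ORR could create a mismatch. The planned Stage 1 look in Protocol 9.6 used first postbaseline scans, so it would not have waited for confirmation either.

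A reader might also infer that the plan confirms progression but not response. Protocol 7.6.1.2 does say "Disease progression should be confirmed at least 4 weeks and not later than 8 weeks after the first scan indicating PD", but this applies to clinically stable subjects and serves the decision to continue treatment. In the analysis, progression is unconfirmed as well: PFS uses the first PD (SAP 7.2.5) and best response stops there (SAP 7.2.2).

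Two further points stand. The visible protocol ORR definition (2.2.1, 9.4.1) has no confirmation rule and part of the response-assessment text is not in the public copy, so exactly what was dropped cannot be seen. The change is also openly declared, and the listings let a diligent reader check persistence subject by subject.

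None of this answers the narrower point: the summary table gives a single-scan ORR without saying so.

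**Conclusion.** The concern holds as a point about a descriptive estimate. The planned ORR is an unconfirmed rate that can only equal or exceed the confirmed rate on the same data, and DOR may include one-scan responses. The direction follows from the definitions alone. The size is unknown, and each response that would not have been confirmed adds 1/n.

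The documents do not support a claim of an inflated false-positive rate, a claim that the ORR must be compared with 3% on confirmed responses, or a claim that a confirming scan exists for every responder. No design figure needs to change. This is a low-cost improvement in reporting, not a flaw that invalidates the analysis.

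**What to change.** In SAP 7.2.2 and Table 2.1.1:

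- Label the current ORR and DOR *unconfirmed*.
- Beside the ORR, as a sensitivity analysis, report the confirmed ORR: CR or PR repeated at the next scheduled scan, with the same denominator, derived from the data behind Listing 2.6.3.
- Show the number of responders with no later evaluable scan as a separate count. Post-treatment imaging stops under Amendment 4, so silently counting these subjects as unconfirmed could bias the confirmed rate downward. With the count shown, a reader can bracket the confirmed rate between C/n and (C + M)/n.

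The cost is one extra derivation and a few table rows, with no new scans or visits. The confirmed rate may come out lower, and it is only as informative as the later scans allow.
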